#### 6.2.3 Safety assessment

The Event eCRF allows for reporting of any adverse events, reporting of unanticipated problems, and reporting of protocol deviations. Local Principal Investigators are responsible for ensuring this form is accurately completed and entered in the web-based data entry system.

#### 6.2.4 Questionnaires and assessments

Research/Clinical assessments: These scales are typically done as a way for the physician or independent evaluator, to measure the aneurysm's effect on the patient. They include Hunt and Hess grade, Fisher scale/WFNS (if applicable), modified Rankin score, and NIH Stroke Scale.

## **7. Safety Monitoring**

### ***7.1 Adverse Events (AEs) Definitions and Reporting Procedures***

#### **7.1.1 Definition**

An adverse event will be considered any undesirable sign, symptom or medical condition considered related to the intervention. Medical condition/diseases present before starting the intervention will be considered adverse events only if they worsen after starting the study and that worsening is considered related to the study intervention. An adverse event is also any undesirable and unintended effect of research occurring in human subjects as a result of the collection of identifiable private information under the research. AEs will be recorded up to the day of the

final follow-up visit, and if still present, they will be recorded as “ongoing” at the end of the study. The occurrence of AEs should be sought by non-directive questioning of the patient at each visit during the study. AEs also may be detected when they are volunteered by the patient during or between visits.

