#### 7.1.3 Reporting

All adverse events must be recorded on the Event eCRF with the following information:

1. Whether it was anticipated
2. Its relationship to the procedure, clinical course of the disease, device, or non-procedure
3. Outcome/Patient status
4. Treatment provided
5. Whether an action was taken and a description of said action

All serious adverse events must also be recorded on the Event eCRF with the following additional information:

6. Type of Serious Adverse Event
7. Whether it was reported within 72 hours of becoming aware of the event
8. Whether it happened during the procedure
9. Background Information
10. Whether it will be reported to the local IRB
11. Territory where initial procedure occurred

12. Whether it was serious (not life threatening), serious (life threatening) or lead to death

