## **7.2 Serious Adverse Events (SAEs) Definition and Reporting Procedures**

### 7.2.1 Definition

1. An SAE will be considered any undesirable sign, symptom, or medical condition which is fatal, life-threatening, requires or prolongs inpatient hospitalization, results in persistent or significant disability/incapacity, constitutes a congenital anomaly or birth defect, is medically significant and which the investigator regards as serious based on appropriate medical judgment. An AE that may not result in death, be life-threatening, or require hospitalization may be considered an SAE when, based upon appropriate medical judgment, may jeopardize the patient and may require medical or surgical intervention to prevent one of the outcomes listed in the definitions of SAEs.

2. The Principal Investigator will report unexpected and serious AEs to the DSMB within 15 working days of notification and all others expeditiously. The DSMB will meet on a semi-annual basis or on ad hoc basis if the PI identifies unusual increases in AEs or unexpected events. The following events require expedited reporting: (1) unexpected serious adverse events (must be both serious and unexpected); (2) peri-procedural death within 30 days of procedure (site PIs may be required to provide additional information on such cases); (3) an increase in the rate of expected SAEs occurring in a center.

3. Events NOT considered to be SAE are hospitalizations for: (1) the routine treatment or monitoring of the studied indication not associated with any deterioration in condition; (2) treatment, which was elective or pre-planned, for a pre-existing condition that is unrelated to the indication under study and did not worsen; (3) admission to a hospital or other institution for general care, not associated with any deterioration in condition; (4) treatment on an emergency, outpatient basis for an event not fulfilling any of the definitions of serious given above and not resulting in hospital admission.

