### 7.2.2 Reporting

1. To ensure patient safety, every SAE, regardless of suspected causality, occurring after the patient has provided informed consent and until the final follow-up visit must be reported to Vanderbilt University Medical Center immediately and within 72 hours of learning of its occurrence.

2. An SAE occurring at a different time point or otherwise considered completely unrelated to a previously reported event should be reported separately as a new event.
3. Information about SAEs will be collected and recorded on the Event Form in the study's electronic database. The investigator must assess the relationship to study intervention and complete the form. This must be completed within 72 hours of discovery for review by the Vanderbilt University Medical Center Study Team.
4. Each re-occurrence, complication, or progression of the original event should be reported as a follow-up to that event regardless of when it occurs. The follow-up information should describe whether the event has resolved or continues and if and how it was treated.

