#### 3.1.2 Randomization and Masking

Patients will be randomly assigned in a 1:1 allocation to receive either larger or smaller coils. Patient randomization will be stratified by clinical site, aneurysm status (recently ruptured versus not), and dome to neck ratio (wide neck versus not). Randomization will be performed centrally through a web-based data collection system that automates the delivery of the randomization assignments.

Investigators will not be blinded to treatment assignment due to the nature of the treatment intervention. Investigators will, however, be blinded to all data from other clinical sites. Clinical outcome assessments will be completed by certified research staff that are not part of the treatment team. All angiograms will be analyzed by a blinded angiogram core laboratory personnel who will be blinded to clinical outcomes. Trial oversight will be provided by an independent Data and Safety Monitoring Board (DSMB).

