#### **6.7.1 *Adverse Events Reporting***

All adverse events, serious and non-serious, will be summarized in tabular form for reporting to the DSMB. Adverse events will be tabulated by seriousness, severity and relatedness to the investigational agent or the aneurysm.

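### Protocol 7.1.1 makes relatedness to the intervention a condition of being an adverse event, so non-serious events judged unrelated may go unrecorded; serious events are not affected

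*Combined protocol and SAP*

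**What the plan says.** Protocol 7.1.1 defines the adverse event: "An adverse event will be considered any undesirable sign, symptom or medical condition considered related to the intervention". Conditions present before the intervention count "only if they worsen after starting the study and that worsening is considered related to the study intervention". The section adds one further category, unintended effects of collecting private information in the research, which does not bear on this point.

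Protocol 7.1.3 then lists what the Event eCRF must hold for all adverse events. One item is "Its relationship to the procedure, clinical course of the disease, device, or non-procedure".

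SAP 6.7.1 covers serious and non-serious events in tables for the DSMB: "Adverse events will be tabulated by seriousness, severity and relatedness to the investigational agent or the aneurysm".

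Serious events have their own rules. Protocol 7.2.1 begins "An SAE will be considered any undesirable sign, symptom, or medical condition which is fatal, life-threatening, requires or prolongs inpatient hospitalization" and sets no relatedness condition. Protocol 7.2.2 requires that "every SAE, regardless of suspected causality, occurring after the patient has provided informed consent and until the final follow-up visit must be reported", and adds: "The investigator must assess the relationship to study intervention and complete the form".

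On masking, SAP 3.1.2 says: "Investigators will not be blinded to treatment assignment due to the nature of the treatment intervention".

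**The concern.** Relatedness is a matter of opinion and is normally recorded about an event that has already been captured. Here it decides whether a non-serious event exists for the trial at all, and the person deciding knows which coils were used.

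A site that follows 7.1.1 to the letter would never use the non-procedure option for a non-serious event, and would have little or no use for the disease-course option. A site that takes its lead from the form would record such events. Both could claim to be following the protocol, so counts of non-serious events would not mean the same thing across sites.

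The tables go to the DSMB. Protocol 7.4 asks that board to consider, among other things, whether a lower recurrence rate comes without a higher risk of adverse events. For non-serious events, that would be a comparison of counts that had already passed through an arm-aware judgement.

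**Working it through.** The plan states no figure on this point, so the main check is to set the provisions side by side.

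| Place | Events covered | Is relatedness a condition of capture? |
|---|---|---|
| Protocol 7.1.1, new events | AEs | Yes |
| Protocol 7.1.1, pre-existing conditions | AEs | Yes, for the worsening |
| Protocol 7.1.3 | All AEs | No; it is a field, with options outside the intervention |
| SAP 6.7.1 | Serious and non-serious AEs | No; it is a dimension of the table |
| Protocol 7.2.1 | SAEs | No |
| Protocol 7.2.2 | SAEs | No; expressly ruled out |

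Applying these to the four kinds of event:

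- Serious, judged related: captured.
- Serious, judged unrelated: captured under 7.2.2.
- Non-serious, judged related: captured.
- Non-serious, judged unrelated: not an adverse event under 7.1.1, although 7.1.3 and SAP 6.7.1 provide a place for it.

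Only the last kind is at risk.

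**Illustration for non-serious events only.** All rates here are assumptions, because the documents give none. Let *r* = 10% be the incidence of truly related events and *u* = 30% that of truly unrelated events, the same in both arms. The true total is 40%. Let *m* be the probability that an unrelated event is judged related, and suppose that all truly related events are judged so. Then:

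- recorded incidence = *r* + *u* × *m*
- share lost = (0.40 − recorded) / 0.40

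| *m*, smaller coils | *m*, larger coils | Recorded, smaller | Recorded, larger | Ratio, larger to smaller |
|---|---|---|---|---|
| 0 | 0 | 0.100 | 0.100 | 1.00 |
| 0.05 | 0.05 | 0.115 | 0.115 | 1.00 |
| 0.05 | 0.10 | 0.115 | 0.130 | 1.13 |
| 0.05 | 0.15 | 0.115 | 0.145 | 1.26 |
| 0.05 | 0.20 | 0.115 | 0.160 | 1.39 |

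For example, in the last row 0.10 + 0.30 × 0.20 = 0.160, and 0.160 / 0.115 = 1.39. If the judgement leaned the other way, the ratio would invert: 0.115 / 0.160 = 0.72.

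In the first two rows the share lost is (0.40 − 0.10) / 0.40 = 75% and (0.40 − 0.115) / 0.40 = 71%, the same in both arms. Equal judgement therefore costs completeness but creates no difference between arms. A difference needs unequal judgement, and the ratios above 1.00 follow directly from the inequality assumed.

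**The case against.** The strongest reply is that the plan protects what it formally analyses. The only safety endpoint in SAP 5.3 is serious adverse events, and the only formal comparison of adverse events, the Poisson model in SAP 6.7.2, is of the same events. Mortality, NIHSS morbidity, mRS, re-hemorrhage and re-treatment are separate endpoints that do not depend on the adverse event definition. All of this stands, and it limits the point to descriptive tables.

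A reader might infer that serious events are filtered too. Protocol 7.1.3 treats them as adverse events with extra fields, and the medical-judgement route in 7.2.1 starts from the term AE. The documents do not support that inference. The opening definition in 7.2.1 stands on its own and already includes medically significant events, 7.1.3 only adds items to the form, and 7.2.2 is an explicit instruction to report serious events whatever their cause. For the same reason it would be wrong to say that the relatedness table as a whole is invalid, or that its unrelated cells must be empty: serious events can properly fill them.

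A reader might also infer that the unblinded judgement does favour one arm. Nothing in the documents shows this. Protocol 7.1.2 lists the risks of angiography with coil embolization, which both arms undergo, so an event can be judged related in either. Unblinding makes unequal judgement possible and no more.

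Finally, the form offers unrelated options and 7.1.1 asks for non-directive questioning, so sites may in practice record unrelated events. That makes the loss uncertain, but it does not remove the contradiction.

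**Conclusion.** The point holds for non-serious events. Protocol 7.1.1 contradicts Protocol 7.1.3 and SAP 6.7.1. If 7.1.1 is followed as written, the non-serious rows of the DSMB table lack events judged unrelated. If sites differ in which text they follow, those rows are not comparable across sites, and they could differ between arms through judgement alone.

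The size cannot be derived from the documents. Under the assumed rates, about 71% to 75% of non-serious events would be lost when judgement is equal, with a ratio of 1.00. The ratio moves away from 1.00 only if judgement differs by arm, and the values of 1.13 to 1.39 illustrate that without being estimates. They rest on the assumed 10% and 30% incidences, the assumed misjudgement probabilities, and strict adherence to 7.1.1.

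Serious events, the SAE endpoint, the Poisson comparison and the primary efficacy analysis are not touched. This is a contradiction in a safety definition that should be corrected, with a limited consequence.

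**What to change.** In Protocol 7.1.1, define an adverse event irrespective of causality by removing the relatedness condition from both sentences, the one on new events and the one on pre-existing conditions. Set the capture window from informed consent to the final follow-up visit. That agrees with 7.2.2 and with the visit schedule in 6.1, which evaluates events from screening and enrollment; a window opening at randomization would contradict both. Keep relatedness as a recorded attribute with the 7.1.3 categories.

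In SAP 6.7.1, tabulate by arm all adverse events first, then by the eCRF relationship categories in place of the agent-or-aneurysm split, with serious and non-serious events shown separately. If non-serious events have already been collected under the present definition, state beside the table that they were subject to the relatedness condition. The SAP's purpose section allows revision before data lock, so this part remains open even if a protocol change comes too late.

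The cost is wording in two documents, with no new form. The downside is that sites will record somewhat more non-serious events.

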#### 7.1.2 Known risks involved in cerebral angiography with coil embolization are:

1. Bleeding
2. Infection
3. Allergic reaction to contrast or medication
4. Hydrocephalus/inflammation
5. Blood vessel injury or thrombosis
6. Kidney damage or failure
7. Stroke
8. Vessel dissection/rupture
9. Aneurysm perforation
10. Clot formation
11. Device malfunction
12. Disruption of clot from aneurysm
13. Distal emboli resulting in stroke
14. Death
15. Paralysis
16. Cardiac arrest
17. Brain damage

#### 7.1.3 Reporting

All adverse events must be recorded on the Event eCRF with the following information:

1. Whether it was anticipated
2. Its relationship to the procedure, clinical course of the disease, device, or non-procedure
3. Outcome/Patient status
4. Treatment provided
5. Whether an action was taken and a description of said action

All serious adverse events must also be recorded on the Event eCRF with the following additional information:

6. Type of Serious Adverse Event
7. Whether it was reported within 72 hours of becoming aware of the event
8. Whether it happened during the procedure
9. Background Information
10. Whether it will be reported to the local IRB
11. Territory where initial procedure occurred

12. Whether it was serious (not life threatening), serious (life threatening) or lead to death

## **7.2 Serious Adverse Events (SAEs) Definition and Reporting Procedures**

### 7.2.1 Definition

1. An SAE will be considered any undesirable sign, symptom, or medical condition which is fatal, life-threatening, requires or prolongs inpatient hospitalization, results in persistent or significant disability/incapacity, constitutes a congenital anomaly or birth defect, is medically significant and which the investigator regards as serious based on appropriate medical judgment. An AE that may not result in death, be life-threatening, or require hospitalization may be considered an SAE when, based upon appropriate medical judgment, may jeopardize the patient and may require medical or surgical intervention to prevent one of the outcomes listed in the definitions of SAEs.

2. The Principal Investigator will report unexpected and serious AEs to the DSMB within 15 working days of notification and all others expeditiously. The DSMB will meet on a semi-annual basis or on ad hoc basis if the PI identifies unusual increases in AEs or unexpected events. The following events require expedited reporting: (1) unexpected serious adverse events (must be both serious and unexpected); (2) peri-procedural death within 30 days of procedure (site PIs may be required to provide additional information on such cases); (3) an increase in the rate of expected SAEs occurring in a center.

3. Events NOT considered to be SAE are hospitalizations for: (1) the routine treatment or monitoring of the studied indication not associated with any deterioration in condition; (2) treatment, which was elective or pre-planned, for a pre-existing condition that is unrelated to the indication under study and did not worsen; (3) admission to a hospital or other institution for general care, not associated with any deterioration in condition; (4) treatment on an emergency, outpatient basis for an event not fulfilling any of the definitions of serious given above and not resulting in hospital admission.

### 7.2.2 Reporting

1. To ensure patient safety, every SAE, regardless of suspected causality, occurring after the patient has provided informed consent and until the final follow-up visit must be reported to Vanderbilt University Medical Center immediately and within 72 hours of learning of its occurrence.

2. An SAE occurring at a different time point or otherwise considered completely unrelated to a previously reported event should be reported separately as a new event.
3. Information about SAEs will be collected and recorded on the Event Form in the study's electronic database. The investigator must assess the relationship to study intervention and complete the form. This must be completed within 72 hours of discovery for review by the Vanderbilt University Medical Center Study Team.
4. Each re-occurrence, complication, or progression of the original event should be reported as a follow-up to that event regardless of when it occurs. The follow-up information should describe whether the event has resolved or continues and if and how it was treated.

### ***7.3 Protocol Deviation***

1. A protocol deviation is defined as any change, violation, or departure from the study design or procedures of research project that is NOT approved by the Vanderbilt University Medical Center or the Trial Steering Committee prior to its initiation or implementation, or deviation from standard operating procedures, Good Clinical Practices, or federal, state, or local regulations. Protocol violations may or may not be under the control of the study team or Vanderbilt University Medical Center staff. These protocol violations may be major or minor and will be recorded in the electronic data capture system.
2. Major protocol deviations: All major deviations must be reported to the Vanderbilt University Medical Center study team and the local IRB (according to local regulations) upon discovering them, and no later than seven calendar days from the time the study team receives knowledge of the event. A major violation meets one or more of the following criteria: (1) represents a serious or continuing failure on the part of the study team to comply with the protocol, standard operating procedures, Good Clinical Practices, federal, state or local regulations; (2) impacts subject safety or substantially alters risks to subjects and may or may not result in actual harm (emotional, clinical, social, financial, etc.); (3) significantly damages the completeness, accuracy and/or reliability of the data collected for the study; (4) is under control of the investigator/study team.

3. Examples of major deviations may include, but are not limited to: (1) evidence of willful or knowing misconduct on the part of the investigators or team; (2) failure to obtain informed consent; (3) enrollment of a subject who did not meet all inclusion/exclusion criteria which would affect subject safety or would negatively impact data integrity; (4) performing study procedures not approved by The Vanderbilt University Medical Center study team or IRB; (5) failure to report serious unanticipated problems or AEs to the IRB and Vanderbilt; (6) failure to perform study procedures outlined in the protocol where subject safety or data integrity may be negatively impacted; (6) study visit or procedure conducted outside of required time frame that may negatively affect subject safety.

#### ***7.4 Data Safety Monitoring Board (DSMB)***

The DSMB will be independent and comprised of neurosurgeons, neuro-interventionalists, or others who are from institutions that are not participating in the trial. The DSMB will meet semi-annually to review any serious unexpected AEs. The DSMB will be supplied with an interim analysis of trial data on mortality/complication rates after the first 70 and 140 patients are randomized. The committee may request data or analyses from the trial or any other relevant information from other sources. In the light of these analyses, the DSMB will advise the Steering Committee if, in its view, the randomized comparisons have provided proof “beyond reasonable doubt” that (1) the use or non-use of Eighteen platinum coils achieves a significantly reduced recurrence rate with no greater risk of AEs, or (2) the use or non-use of Eighteen platinum coils is associated with a substantially poorer clinical outcome. The DSMB will advise the Steering Committee regarding trial continuation or discontinuation, or protocol modification as needed to address patient safety concerns. A third interim analysis will be performed after 380 patients have been randomized (unless the DSMB decides the interim analysis should occur earlier or later). Site PIs and study coordinators will have the name and address of the DSMB chairman, and will be able to communicate confidentially with the chairman to express concerns about patient safety or trial design.

## **8. Data Management and Entry**

### ***8.1 Data Collection***

1. Each site will be required to have a local coordinator who will be responsible for entering the study information into the web-based database and uploading the identifiable source documents/medical records associated with the study information. A web-based database housing the electronic case report forms (eCRFs) has been designed for the study, which will improve efficiency, lower cost of the study, and speed up publication of the results. Use of drop-down selection lists, radio buttons, checkboxes, and validation

checks will be incorporated to aid the speed, accuracy and consistency of data entry. The database will be backed up regularly.

2. Data collected will include: (1) enrollment and screening logs; (2) demographic data; (3) admission data (Hunt and Hess grade, Fisher grade, etc.) including the informed consent; (4) procedural data; (5) angiograms or MRA; (6) clinical course data; (7) 3-6 month angiogram or MRA; (8) 3-6 month clinical status; (9) 12-18 month angiogram or MRA; (10) 12-18 month clinical status; and (11) as needed additional follow-up data.

3. All data other than angiograms will be entered and/or uploaded into the web-based data entry forms. In addition, identifiable source documentation verifying all collected study data points will be securely uploaded into the web-based database.

